4 DEFINING PRESYNCOPE AND SYNCOPES

4.1 Presyncope

For this study, the case definition of presyncope was based on review of the literature, the Blood Donations Reactions Inventory (BDRI), expert opinion, and prior experience with the hydration study.¹²⁻¹⁴ Although there may be measurable physiological changes with presyncope (e.g., decrease in heart rate or blood pressure), there are no established cut-offs that define presyncope. Therefore, the case definition is based on subjective criteria. The case definition previously used in Oral Water Hydration to Prevent Post-Vaccination Presyncope (“Water and Vaccines Study”) is below:

Sudden onset of one or more of the following symptoms or signs during the post-vaccination observation period in the clinic:

Symptoms

- Feeling lightheaded, like you might “pass out” or faint
- Feeling dizzy, like the room is spinning
- Feeling weak
- Feeling like your face is getting red and warm (or hot), like blushing or flushing
- Noticing any change in your vision, like spots or flickering lights, tunnel vision, or loss of vision
- Experiencing ringing in your ears, decreased hearing, or sounds seem far away
- Feeling like your heart is beating fast or hard or pounding
- Feeling hot AND sweaty
- Feeling cold AND sweaty, or “clammy”
- Feeling like you are breathing fast or hard
- Feeling like you might throw up (nausea)

Signs

- Pallor
- Sweaty
- Facial flush
- Decreased interactivity (decreased level of arousal or responsiveness)

AND

- Not Syncope
- Not Due to another Cause
- Not clearly present at baseline

For the purpose of this study, presyncope will be defined as any response of self-report of “some,” or “a lot,” to the modified BDRI or study staff noting signs or symptoms on study documents if the subject requires medical attention and does not complete the BDRI form

Usual clinical care will be provided to any subject who develops presyncope.

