4.2 Syncope

Syncope (fainting) that occurs in an otherwise healthy person after receipt of a vaccine or during venipuncture is usually attributed to vasovagal syncope, and may occur alone (simple syncope) or may be associated with tonic-clonic movements (convulsive syncope, anoxic seizure).^{12,13} For the purposes of this study, we have defined syncope as: Any sudden and brief loss of consciousness or postural tone after vaccination from which recovery is spontaneous and is not attributed to another cause (e.g., anaphylaxis). For purposes of this study, cases counted as syncope must occur during the post-vaccination observation period.

Usual clinical care will be provided to any subject who develops syncope.

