7.12 Presyncope and Syncope

At 15 minutes (up to 20 minutes) following vaccination, study participants will complete the BDRI. During the 20 minute (up to 25 minute) observation period, research staff will also record any observed signs (pallor, sweating, facial flush or decreased interactivity) or spontaneous subject reports of symptoms of witnessed presyncope as described in Section 4.1. Subjects who developed post-vaccination syncope as described in Section 4.2 regardless of presyncope are classified as having syncope. Usual clinical care will be provided to any subject who develops presyncope or syncope.

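### Does the presyncope rule in Section 4.1 let EOM 1.1 count symptoms that were already there before the injection?

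*Combined protocol and SAP*

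**What the plan says.** Section 4.1 contains two texts. The first is introduced as "The case definition previously used in Oral Water Hydration to Prevent Post-Vaccination Presyncope" and calls for "Sudden onset of one or more of the following symptoms or signs during the post-vaccination observation period in the clinic". It lists symptoms and four signs, then adds exclusions, among them "Not Due to another Cause" and "Not clearly present at baseline". The second is the rule for this pilot: "For the purpose of this study, presyncope will be defined as any response of self-report of" *some* or *a lot* on the modified BDRI. Staff notes of signs or symptoms take its place when a participant needs medical attention and does not complete the form.

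Section 4.2 handles syncope in a single text: "For the purposes of this study, we have defined syncope as: Any sudden and brief loss of consciousness or postural tone after vaccination". It rules out other causes and adds that "cases counted as syncope must occur during the post-vaccination observation period".

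Section 7.12 schedules the BDRI at 15 (up to 20) minutes. It also has staff record observed signs and "spontaneous subject reports of symptoms of witnessed presyncope as described in Section 4.1". Table 1 has no symptom inventory before vaccination. EO1, EOM 1.1 and the analysis text in Section 8.2.5 limit the outcome only by saying that it occurs after vaccination.

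**The concern.** The pilot's own rule is shorter than the definition printed above it, and no sentence says whether the longer definition's conditions carry over. Section 4.2 shows that the authors could write such limits into a study-specific definition when they chose to.

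Several listed symptoms, such as a pounding heart, fast breathing, weakness and nausea, are ones an anxious adolescent may feel while waiting for the needle. Section 1.1 names higher pre-vaccination anxiety as a risk factor for presyncope. With a single BDRI after the injection, a persisting symptom rated *some* could be scored as presyncope. The proportion would then be too high for an objective about presyncope following vaccination, and if onset is not recorded it could not be corrected later. The same definition might also be carried into the larger trial.

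**Working it through.** No arithmetic decides this point, so the texts come first and the scale second.

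**Step 1. The conditions side by side.**

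| Condition | Listed definition (4.1) | Study rule (4.1) | Syncope (4.2) |
|---|---|---|---|
| Sudden, within the observation period | stated | not stated | stated |
| Not due to another cause | stated | not stated | stated |
| Not clearly present at baseline | stated | not stated | not stated |
| Not syncope | stated | not stated, but settled in 7.12, where syncope takes precedence | not applicable |

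The silence on the first three conditions is real for the BDRI route.

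**Step 2. How the rest of the protocol uses the list.** Section 4.1 opens by saying that this study's case definition draws on several sources, including experience from the hydration trial. Section 7.12 names four signs for staff to record: paleness, sweating, flushing and reduced interaction. In Section 4.1 these four appear only in the list taken from the earlier trial, so that list is in use here, at least for witnessed presyncope. Sections 4.1 and 7.12 also speak of participants who develop presyncope, which points to new symptoms. The natural reading is that the list gives the concept and *some* or *a lot* sets how strong a self-report must be. This is an inference; no sentence states it for the BDRI.

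**Step 3. What an analyst could do with the data.**
- If the BDRI form asks about feelings since the shot, the onset question is largely answered at collection.
- If the form neither limits nor records onset, every analyst has only the ratings and will count *some* or *a lot* in the same way.

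Disagreement between analysts needs onset information on the forms. A count that cannot be corrected needs its absence. Both harms cannot hold in full together.

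**Step 4. Scale.** The plan gives no expected presyncope rate, so there is no event figure to reproduce. The minimum age stratum does reproduce: 20% (Section 5) × 30 = 6, as in Section 7.8. The weight of one reclassified participant at full enrolment is:
- per arm: 30 / 3 = 10, so 1/10 = 10.0 points;
- overall: 1/30 = 3.3 points;
- smallest age stratum: 1/6 = 16.7 points; the other stratum is then 30 − 6 = 24, so 1/24 = 4.2 points.

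These are the weights of one person in any yes/no outcome of this pilot, not evidence of bias. For illustration, let *q* be the share of participants whose symptom predates the injection and is still reported. The documents do not give *q*. The chance of at least one such participant in an arm of 10 is 1 − (1 − *q*)^10, and the expected number among 30 is 30*q*:

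| assumed *q* | at least one in an arm of 10 | expected among 30 |
|---|---|---|
| 2% | 18% | 0.6 |
| 5% | 40% | 1.5 |
| 10% | 65% | 3 |
| 20% | 89% | 6 |

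Some inflation is therefore possible, but the range is too wide to support a conclusion. Section 6.2 lowers *q* to some extent by excluding febrile or acutely ill adolescents and those with a blood draw or medication injection in the past hour.

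**Step 5. What a stricter rule would cost.** Suppose each BDRI item also asked whether the symptom began before or after the shot, and only later onset counted. A symptom that was mild beforehand and became severe afterwards would be dropped. So would symptoms arising between randomisation and the injection, when the interventions are already running. Answers of not sure would need an arbitrary coding, onset would be recalled over 15 to 20 minutes, and other causes would still not be excluded. The literal rule avoids these losses.

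**The case for a change.** The strongest case for acting is that clarity is nearly free. One sentence would settle whether the conditions apply, and onset that was never asked about cannot be recovered. Duke collects the data and CDC leads the analysis from coded records (Section 8.4), so a written rule helps. Baseline pulse and blood pressure cannot replace a symptom question, since Section 4.1 says there are no accepted physiological cut-offs. Even if the form limits answers to new symptoms, the other-cause condition stays unstated. A pilot is also the natural place to settle a definition before a larger trial.

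Much of this stands. The silence is genuine, carry-over is plausible, and a clarifying sentence would do no harm. What does not stand is the step from silence to a flaw in the estimate. That step depends on the wording of a form that is not in the text available, and its absence from that text cannot be held against the plan. Nor is there any demonstrated effect on what the pilot is meant to deliver. Carry-over present before randomisation should be similar across arms on average, and a later effectiveness trial would have its own protocol in which to fix the definition.

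**Conclusion.** No change to the plan is called for. Section 4.1 leaves a gap in wording that analysts can fill sensibly: either the list's conditions are understood as the concept behind the BDRI threshold, or the threshold is applied literally, which for BDRI self-reports gives one reproducible proportion. Whether any pre-injection symptom would be counted depends on the unseen form.

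The possible shift is 10 points per reclassified participant in an arm of 10 and 3.3 points overall, with an unknown number reclassified. It would fall on an exploratory, descriptive outcome in a study that Section 8.1 says is not powered. Sections 1.2 and 5 base the choice of intervention for the larger trial on feasibility and acceptability, and nothing in the plan uses the presyncope rate for sizing. This conclusion assumes full enrolment with equal arms, and that EOM 1.1 is reported as a description rather than as evidence of effectiveness.

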4.2 Syncope

Syncope (fainting) that occurs in an otherwise healthy person after receipt of a vaccine or during venipuncture is usually attributed to vasovagal syncope, and may occur alone (simple syncope) or may be associated with tonic-clonic movements (convulsive syncope, anoxic seizure).^{12,13} For the purposes of this study, we have defined syncope as: Any sudden and brief loss of consciousness or postural tone after vaccination from which recovery is spontaneous and is not attributed to another cause (e.g., anaphylaxis). For purposes of this study, cases counted as syncope must occur during the post-vaccination observation period.

Usual clinical care will be provided to any subject who develops syncope.

5 STUDY DESIGN

This pilot study is a prospective, randomized, open-label clinical trial that will be conducted in adolescents (10-17 years of age) receiving at least one recommended intramuscularly administered vaccine to evaluate the feasibility and acceptability of using two different interventions that might prevent post-vaccination presyncope, and by extension syncope. The two interventions to be evaluated are 1) Buzzy® Drug Free Pain Relief which is a medical device designed to reduce vaccination pain and 2) Listening to music as a distraction technique. We will also evaluate both interventions when administered simultaneously (Buzzy® and music). We will enroll approximately 30 subjects into this pilot study. Eligible adolescents will be randomized (1:1:1) to receive one of the three above named interventions: 1) Buzzy® alone; 2) Music alone; or 3) Buzzy® and Music together to assess for feasibility and acceptability. Eligible adolescents must have an identified risk factor for the development of presyncope including being either of younger age (10-13 years) or receiving 2 or more injectable vaccines (one of which must be received intramuscularly). A minimum of 20% of adolescents enrolled across all intervention groups will be 10-13 years of age and a minimum of 20% of adolescents enrolled across all intervention groups will be 14-17 years of age. Detailed data will be collected and described from study participants including demographics, medical history, baseline anxiety, and needle phobia. Participants will be observed for 20 minutes following receipt of vaccines and reassessed for post-vaccination anxiety, immediate and subsequent post-vaccination pain (within 1 minute and at 10 minutes), the occurrence of witnessed syncope or presyncope, and presyncopal symptoms as rated by the modified BDRI. For the primary objective, we will assess the acceptability and feasibility of both interventions separately or together. For the exploratory objectives, we will assess presyncope symptoms following vaccination, post-vaccination pain, and change in anxiety from baseline for the adolescents randomized to each of the intervention groups. Using lessons learned during the Pilot, if feasible and acceptable, we will evaluate the most feasible and acceptable presyncope prevention strategy in a larger effectiveness trial.

6 STUDY ENROLLMENT AND WITHDRAWAL

Subject Inclusion and Exclusion Criteria will be reviewed at Visit 1 to assess eligibility for study participation.

6.1 Subject Inclusion Criteria

Subjects who meet all of the following criteria will be eligible to participate in this interventional study.

1. 10 years through 17 years of age
2. If 10 through 13 years of age, the subject must be receiving at least one vaccine delivered intramuscularly
3. If 14 through 17 years of age, the subject must be receiving at least two injectable vaccines one of which must be delivered intramuscularly
4. The parent/guardian must be willing and capable of providing written informed consent for the adolescent and the adolescent must be willing and capable of providing assent.
5. The subject must be willing to stay for the completion of all study-related activities.
6. Parent/guardian and adolescent must speak and read English by self-report

6.2 Subject Exclusion Criteria

Subjects who meet any of the following criteria will not be eligible to participate in this study:

1. Receipt of investigational or experimental vaccine or medication within the previous two weeks
2. Receipt of routine injectable medication
3. Permanent indwelling venous catheter
4. Blood drawn within the past hour or scheduled for a blood draw during the post-vaccination observation period
5. Injection of medication during the past hour or scheduled for injection of medication during the observation period.
6. Cold intolerance or cold urticaria
7. Raynaud's phenomenon
8. Sickle cell disease
9. Inability to hear
10. Significant visual impairment or blindness
11. Febrile or acutely ill individuals
12. Upper arm or shoulder pain or injury
13. Adolescent or parent/Guardian is an immediate relative of study staff or an employee who is supervised by study staff.
14. Any condition that would, in the opinion of the site investigator, place the participant at an unacceptable risk of injury or render the participant unable to meet the requirements of the protocol

6.3 Recruitment

The 30 participants in this study will be male or female adolescents 10 to 17 years of age. Adolescents will be recruited from designated study sites affiliated with the Duke University Health System (Duke Children's Primary Care, Durham Pediatrics, and Regional Pediatrics). Adolescents will primarily be recruited at the time of well child visits.

6.4 Reasons for and Handling of Withdrawals

The following may be reasons for study withdrawal:

- As deemed necessary by the principal investigator (PI).
- Parent(s)/Legally Authorized Representative(s) (Guardian(s)) withdrawal of permission for their adolescent to participate.
- Termination of the study by the sponsor.

A parent/Guardian may withdraw permission for their adolescent to participate at any time and for any reason, without penalty. Subjects who are withdrawn from the study prior to randomization or intervention will be replaced. Subjects who are withdrawn from the study after receiving intervention will not be replaced. For subjects who received intervention, data collected prior to withdrawal in the study will be included in the study.

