 8.2.2 Descriptive Statistics27

 8.2.3 Primary Objective (PO) 1:.....27

 8.2.4 Primary Objective (PO) 2:.....28

8.2.5 *Exploratory Objective (EO) 1*: 28
8.2.6 *Exploratory Objective (EO) 2*: 29
8.2.7 *Exploratory Objective (EO) 3*: 30
8.3 DATA MANAGEMENT 30
 8.3.1 *Research Electronic Data Capture (REDCap)*..... 30
8.4 ROLE OF THE CDC INVESTIGATORS IN THE PROJECT 31
9 HUMAN SUBJECTS 32
 9.1 HUMAN SUBJECTS INVOLVEMENT, CHARACTERISTICS, AND DESIGN..... 32
 9.2 SOURCES OF MATERIAL 32
 9.3 POTENTIAL RISKS AND BENEFITS..... 32
 9.4 ADEQUACY OF PROTECTION AGAINST RISKS 32
 9.4.1 *Protections against Risk*..... 32
 9.4.2 CLINICALTRIALS.GOV REQUIREMENTS..... 33
 9.5 HUMAN SUBJECTS..... 33
 9.5.1 *Vulnerable Subjects Research*..... 33
10 REFERENCES..... 34

PROTOCOL SUMMARY

Title:	Preventing Post-Vaccination Presyncope and Syncope in Adolescents Using Simple, Clinic-based Interventions: A Pilot Study
Population:	Up to 30 adolescents, 10 to 17 years of age, who will receive at least one intramuscularly administered vaccine
Clinical Sites:	One: Duke University
Study Duration:	6 weeks
Participant Duration:	1 day
Description of Study Procedures:	This is a randomized controlled open-label trial. During the study, adolescents scheduled to receive at least one IM vaccine will receive either Buzzy®, Music, or Buzzy® and Music intervention(s) in addition to standard care to evaluate the feasibility and acceptability of these interventions prior to being used in a larger study to assess the effectiveness of the interventions in preventing post-vaccination presyncope and syncope. Feasibility will be assessed according to study staff ability to successfully administer the protocol specified clinic-based interventions and per both study staff and healthcare provider responses to written feasibility assessments. Acceptability will be assessed according to the participant's self-report. In addition, baseline needle phobia and anxiety, post-vaccination pain and presyncope symptoms, and pre- and post- vaccination state anxiety will be assessed per participant written self-report to standardized survey questions.

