8.2 Analysis Plan

8.2.1 Study Populations

The study will enroll adolescents, female and male, ages 10-17 years, receiving at least one ACIP recommended vaccine administered intramuscularly administered. Participants will be randomized into one of three intervention groups: Buzzy® only, Music only, Buzzy® and Music together.

There will be two study populations used for data analysis in this study. These are defined below:

- Intent-to-treat (ITT) population: is defined as those subjects who are randomized and have received at least one dose of an intramuscularly administered vaccine.
- Per-protocol population: is defined as those subjects who are randomized, have received at least one dose of an intramuscularly administered vaccine, have completed study procedures including all surveys post-vaccination through the 20-minute time-period, and have no protocol violations that are likely to affect the objectives.

The primary and exploratory objective analyses will be performed in the ITT and per-protocol populations, or only the ITT population if no subject is excluded from the per protocol population. The primary and exploratory objective analyses will be performed by intervention group and age group (10-13 and 14-17), as appropriate.

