8.2.2 Descriptive Statistics

Descriptive analyses will be conducted for demographic variables and for baseline characteristics (e.g., fatigue, hunger, thirst, and PROMIS score). Continuous variables will be summarized with standard descriptive statistics including means, medians, ranges, and standard deviations. Categorical variables will be summarized with frequencies and percentages. Ninety-five percent confidence intervals will be provided for descriptive statistics, as warranted. Figures will be provided to evaluate the data distribution. The descriptive statistics will be analyzed in the ITT and per-protocol population, accordingly.

8.2.3 Primary Objective (PO) 1:

To assess the feasibility of using simple clinic-based interventions (Buzzy® alone, music alone, or Buzzy® and music together) to inform the development of a larger study designed to assess the effectiveness of the interventions in preventing post-vaccination presyncope in adolescents

Primary Objective Measure (POM) 1.1: The proportion of adolescents meeting each feasibility benchmark

- Assess the proportions of those achieving each feasibility benchmark (**Appendix C**) within each intervention group and overall, as applicable. A descriptive summary of findings by age group will also be conducted, as appropriate.

Primary Objective Measure (POM) 1.2: Descriptive results of feasibility survey among study coordinators

- Assess study coordinator feasibility questionnaires for each survey question by intervention group and by age group. Percentages, means and/or medians will be presented. A descriptive summary of qualitative responses will also be presented.

Primary Objective Measure (POM) 1.3: Descriptive results of feasibility survey among study healthcare providers

- Assess healthcare provider feasibility questionnaires for each survey question by intervention group and by age group. Percentages, means and/or medians will be presented. A descriptive summary of qualitative responses will also be presented.

8.2.4 Primary Objective (PO) 2:

To assess the acceptability of using simple clinic-based interventions (Buzzy® alone, music alone, or Buzzy® and music together) to inform the development of a larger study designed to assess the effectiveness of the interventions in preventing post-vaccination presyncope in adolescents

Primary Objective Measure (POM) 2: Descriptive results of study intervention acceptability surveys among study adolescents

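### A participant who leaves between randomisation and intervention and is not vaccinated is replaced and lies outside both analysis sets, so POM 1.1 could overstate delivery feasibility (minor)

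*Combined protocol and SAP*

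**What the plan says.** Section 6.4 sets the replacement rule: "Subjects who are withdrawn from the study prior to randomization or intervention will be replaced". Those withdrawn after the intervention are not replaced. Retention of data is promised for that second group only: "For subjects who received intervention, data collected prior to withdrawal in the study will be included in the study".

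Section 8.2.1 defines two analysis sets. The ITT set "is defined as those subjects who are randomized and have received at least one dose of an intramuscularly administered vaccine". The per-protocol set adds completion of the post-vaccination procedures and absence of relevant violations. On their use, the section says: "The primary and exploratory objective analyses will be performed in the ITT and per-protocol populations". No all-randomised set is defined.

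For POM 1.1, section 8.2.3 says: "Assess the proportions of those achieving each feasibility benchmark", by intervention group and overall. It refers to Appendix C for the benchmarks and states no denominator of its own. The Protocol Summary gives the meaning of feasibility: "Feasibility will be assessed according to study staff ability to successfully administer the protocol specified clinic-based interventions", and also "per both study staff and healthcare provider responses to written feasibility assessments".

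**The concern.** The step between randomisation and the start of the assigned intervention is where a failure to deliver can first appear. If a participant is lost there and is not vaccinated, the plan takes that person out of the primary analysis and enrols someone else. POM 1.1 is the count-based part of the feasibility assessment, and the lost case could be one of the failures it is meant to count.

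The loss need not be equal across arms. Assignment is open (section 7.8.1), permission can be withdrawn at any time (section 6.4), and section 9.3 foresees discomfort specific to an intervention, from cold or from music volume. Feasibility, together with acceptability, is to decide which strategy goes into the larger trial (sections 1.2 and 5). An upward shift confined to one arm would therefore enter that choice.

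**Working it through.** **Step 1: apply the definitions.** Section 7.1 orders the visit as randomisation, intervention, vaccination. Three kinds of participant follow.

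| Randomised | Intervention | IM vaccine | Replaced (6.4) | In ITT set (8.2.1) |
|---|---|---|---|---|
| yes | no | no | yes | no |
| yes | no | yes | yes | yes |
| yes | yes | yes | no | yes |

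Only the first row leaves the POM 1.1 denominator. The per-protocol set is contained in the ITT set, so it does not recover that participant.

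**Step 2: inputs for size.**
- Total of 30: section 8.1, which gives it as an upper limit and says the study is not powered. There is no power or precision figure to reproduce.
- 1:1:1 allocation: sections 5 and 7.8. Arms of 30/3 = 10 are assumed from this.
- k, the number of such departures in one arm: not given. Assumed range 0 to 3.
- All other participants are assumed to meet the benchmark, and each departure is counted as not delivered. This is an upper illustration, since some departures will not be delivery failures.

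**Step 3: formula.** As written, the proportion is x/n. In all randomised participants it is x/(n + k). For the arm, n depends on where the replacements go. Section 6.4 does not say, and with permuted blocks (section 7.8) a replacement may fall in any arm. If all join the same arm, n = 10; if all join other arms, n = 10 − k. Overall, n = 30 in either case.

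| k | Arm, replacements in same arm | Arm, replacements elsewhere | Overall |
|---|---|---|---|
| 0 | 10/10 = 100%, no change | 10/10 = 100%, no change | 30/30 = 100%, no change |
| 1 | 10/10 = 100% to 10/11 = 90.9% | 9/9 = 100% to 9/10 = 90.0% | 100% to 30/31 = 96.8% |
| 2 | 100% to 10/12 = 83.3% | 8/8 = 100% to 8/10 = 80.0% | 100% to 30/32 = 93.8% |
| 3 | 100% to 10/13 = 76.9% | 7/7 = 100% to 7/10 = 70.0% | 100% to 30/33 = 90.9% |

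**Step 4: precision.** Exact (Clopper-Pearson) 95% intervals for one departure, replacement in the same arm: 10/10 gives 69.2 to 100, 10/11 gives 58.7 to 99.8. Overall: 30/30 gives 88.4 to 100, 30/31 gives 83.3 to 99.9. Each shifted proportion lies inside the interval of the unshifted one.

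**Step 5: unrelated departures.** With two departures in one arm, one of them unrelated to the intervention, and both replaced in that arm, the proportion is 10/12 = 83.3% with the unrelated case and 10/11 = 90.9% without it. Reasons therefore matter to the result.

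**The case against.** The strongest reply is that the mechanism mostly misses the excluded case. Participants come for vaccines they are due, mainly at well child visits (section 6.3), and clinic staff give those vaccines outside the study procedures (section 7.1). Someone who dislikes the assigned arm has no evident reason to forgo the vaccine and, once vaccinated, is in the ITT set. Those who go unvaccinated may have refused the vaccine, which says little about delivery. Participants must also be willing to stay for the whole visit (section 6.1). This stands, and it makes the case infrequent. It does not remove it, because section 6.4 itself provides for withdrawal in this window.

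Second, Appendix C is not in the supplied text and may set a denominator for each benchmark. This also stands. Sections 7.14 and 8.2.3 do not indicate a different denominator, but one cannot be ruled out.

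Third, rejection of an arm might be called acceptability rather than feasibility. That is partly right, although section 7.14 brings participant compliance into feasibility. The listed grounds for withdrawal also include an investigator decision and "Termination of the study by the sponsor", neither of which need be a delivery failure. Reasons should therefore be shown, and they may be missing, since a parent may withdraw for any reason.

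That every shift lies within the exact intervals is a weaker reply. In a descriptive pilot the reported proportion is itself the result.

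A reader might infer that everyone who leaves after randomisation and before the intervention is lost to the analysis, or that replacement in itself removes a participant. The documents support neither: membership of the ITT set turns on randomisation and vaccination, and section 6.4 does not say that a replaced participant leaves it.

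**Conclusion.** The point holds in a narrow form. On the supplied text, a randomised, untreated and unvaccinated participant is replaced and excluded from both sets used for POM 1.1, so delivery feasibility could be overstated. That exclusion follows directly from the wording of sections 6.4 and 8.2.1. What is unknown is how often it happens and how often it reflects failed delivery.

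One departure counted as a failure moves an arm by 9.1 points (replacement in the same arm) or 10.0 points (replacement elsewhere), and the overall figure by 3.2 points. These sizes rest on arms of 10, success in everyone else, and an assumed count; at zero there is no effect. It would go too far to say that the pilot's feasibility result is biased or that the choice of strategy would change: the documents give no withdrawal rate, the supplied text shows no threshold that would be crossed, and the choice also draws on the coordinator, provider and acceptability surveys. Priority: minor.

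**What to change.** - **Section 8.2.3:** report the POM 1.1 intervention-delivery benchmarks in all randomised participants by assigned arm. Keep replaced post-randomisation withdrawals in the denominator and tabulate them by arm, with the reason where one is given. Also show the proportion without withdrawals known to be unrelated to the intervention.
- **Sections 6.4 and 8.2.1:** state that replacement does not remove a randomised participant from this denominator.
- **Appendix C:** if it already sets denominators, align it and cross-refer from section 8.2.3.
- **Leave unchanged:** the randomised-and-vaccinated set for EO1 to EO3 and for benchmarks on completion of post-vaccination assessments.

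The cost is wording, and a reason field if the case report form has none. No new measurement is needed, because randomisation runs through REDCap (section 7.8) and intervention start and stop times are already recorded (sections 7.9.1 to 7.9.3). The downsides are that stated feasibility may be slightly lower, two versions of the proportion are reported, reasons may be missing for some withdrawals, and the randomised total may exceed 30.
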